3.6.4.2. Physical Exam

Physical exam findings at screening will be documented in medical history. Post baseline physical examination findings, including unscheduled visits, may be reported as adverse events using the protocol adverse event definition.

3.6.4.3. Electrocardiogram Results

The observed data at baseline and change from baseline for each measurement day will be summarized with descriptive statistics by treatment group.

The overall ECG assessment based upon PI assessment will be summarized including post treatment ECGs determined to be abnormal clinically significant.

The absolute QTcF values provided by the core lab will be analyzed as a categorical variable. Each QTcF value in a given patient will be grouped into 4 categories:

- QTcF interval < 450 msec
- QTcF interval 450 - 480 msec
- QTcF interval > 480 - 500 msec
- QTcF interval > 500 msec

The changes in QTcF measures will also be analyzed as categorical variables. The change in QTcF in a given patient will be grouped into 2 categories:

- QTcF interval increases from baseline > 30 msec
- QTcF interval increases from baseline > 60 msec

The overall ECG assessment will be summarized along with a summary of how many subject developed a post treatment abnormal clinically significant result. Denominators for percentages will use the number of assessments available at each visit.

3.6.5. Immunogenicity Data Analysis

Analyses will be conducted using treatment group that the subjects actually received for safety population. Analysis of specific anti-ALD403 antibodies is restricted to subjects who are treated with anti-ALD403.

For subjects with pre-existing antibodies at baseline, the number and percent of subjects who are positive for anti-ALD403 antibody will be summarized. In addition, the number and percent of subjects who develop anti-drug antibodies to ALD403 during the trial will be summarized at each scheduled visit in the same table. Denominators for percentages will be the total number of samples taken for the specified visit.

All the immunogenicity data will be listed.

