2.2. Clinical Trial Endpoints

The efficacy, safety, pharmacokinetic and immunogenicity of ALD403 will be assessed using the following endpoints. Greater detail concerning these endpoints can be found in Section [2.2.2](#).

Primary Efficacy Endpoint

- Change in frequency of migraine days (Weeks 1-12)

Key Secondary Efficacy Endpoints

- 75% migraine responder rate (Weeks 1-4)
- 75% migraine responder rate (Weeks 1-12)
- 50% migraine responder rate (Weeks 1-12)
- Percentage of subjects with a migraine on the day after dosing
- Reduction in migraine prevalence from baseline to Week 4
- Headache Impact Test (HIT-6)
- Acute Migraine Medication Usage

Other Secondary Efficacy Endpoints

- Headaches/migraines with acute medication usage
- Change in frequency of migraine days (Weeks 1-24)
- 100% migraine responder rate (Weeks 1-12)
- Migraine responder rates for time periods other than Weeks 1-12

- Change in frequency of migraine days between baseline and time periods other than Weeks 1-12
- Headache responder rates
- Change in the frequency of headache days
- Percent change in headache or migraine days
- Time to first migraine after dosing
- Headache/migraine hours
- Headache/migraines with severe intensity
- Patient Global Impression of Change (PGIC)
- Short-Form Health Survey (SF-36 v 2.0)
- Health-Related Quality of Life (EQ-5D-5L)

Tertiary Endpoints

- Headache episodes/migraine attacks
- Migraine symptom-free days
- Most Bothersome Symptom (MBS)
- Migraine Free Days

Safety Endpoints

- Adverse events (AEs) and serious adverse events (SAEs)
- Clinical laboratory assessments
- Vital signs
- Electrocardiograms (ECGs)
- Columbia-Suicide Severity Rating Scale (C-SSRS)

Pharmacokinetic Endpoints

- Free ALD403 plasma concentrations

Immunogenicity Endpoints

- Development of specific anti-ALD403 antibodies
- Characterization of specific anti-ALD403 antibodies for neutralizing activity

2.2.1. eDiary

Subjects will complete a daily headache eDiary from the time of screening to Week 24. The diary includes two separate functionalities. The evening report is completed each trial day whether or not the subject had a headache. Among other items this evening report is where

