2.2.4. Immunogenicity

Serum blood samples will be taken pre-dose on Day 0, and Weeks 2, 4, 8, 12 (pre-dose), 24, and 32 or ET to test for the development of antibodies to ALD403. The immunogenicity will be assessed in serum from all ALD403-treated subjects using a validated assay. Immunogenicity will not be assessed in placebo subjects.

For any samples that are positive for anti-ALD403 antibody, there may be additional testing to characterize the anti-ALD403 antibody for the potential to neutralize (NAb) ALD403 activity. Subjects who test positive for specific anti-ALD403 antibodies at the time of the last study visit will be asked to provide up to 2 additional blood samples for immunogenicity testing at 3 month intervals for up to 6 months. See the blinding plan for details concerning blinding and the capture of these samples.

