2.4. Trial Day

Trial endpoints will be reported within analysis windows or analysis intervals based upon the actual date of the assessment. Assignment of results to these time points is based upon the trial day. Trial day is defined as:

$$\text{Trial day} = \text{date of assessment} - \text{date of treatment}$$

Analysis Windows used to report non-diary endpoints are outlined in [Table 3](#).

Table 3: Analysis Windows

Visit	Range	Target Day	If more than one which one is used for analyses
Screening	< Day 0		First value
Day 0	Day 0 to Day 9	Day 0	Closest to Target Day
Week 2	Day 10 to Day 21	Day 14	Closest to Target Day
Week 4	Day 22 to Day 42	Day 28	Closest to Target Day
Week 8	Day 43 to Day 70	Day 56	Closest to Target Day
Week 12	Day 71 to Day 98	Day 84	Closest to Target Day
Week 16	Day 99 to Day 126	Day 112	Closest to Target Day
Week 20	Day 127 to Day 154	Day 140	Closest to Target Day
Week 24	Day 155 to Day 203	Day 168	Closest to Target Day
Week 32	> Day 204	Day 224	Closest to Target Day

Note: If two observations exist with same distance to target day, use first observation.

For the eDiary data used to produce the migraine and headache endpoints the intervals specified in Table 4 will be used to collapse the daily data into 4, 12, and 24 week intervals. For these data baseline is defined as the 28 days starting on the day of the first diary entry.

Table 4: eDiary Headache/Migraine Endpoint Analysis Intervals

Diary Weeks	Trial Time	Comments	Endpoints
Baseline	The 28 days starting from the first eDiary entry		All eDiary related endpoints
1-4	Days: 0-27	Day 0 = First day of treatment	All eDiary related endpoints
5-8	Days: 28-55		All eDiary related endpoints
9-12	Days: 56-83		All eDiary related endpoints
1-12	Weeks 1-4, 5-8, and 9-12	Average of the 4 week intervals after imputation methods are applied	All Primary and Secondary eDiary related endpoints
13-16	Days: 84-111		All eDiary related endpoints
17-20	Days: 112-139		All eDiary related endpoints
21-24	Days: 140-167		All eDiary related endpoints
13-24	Weeks 13-16, 17-20 and 21-24	Average of the 4 week intervals after imputation methods are applied	All Primary and Secondary eDiary related endpoints
1-24	Weeks 1-4, 5-8, 9-12, 13-16, 17-20 and 21-24	Average of the 4 week intervals after imputation methods are applied	All Primary and Secondary eDiary related endpoints

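### SAP 3.6.5 specifies no any-time antibody incidence, keeps baseline positives in the denominator, and lets follow-up samples from positives only fill the Week 24 and Week 32 windows

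*SAP*

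**What the plan says.** The endpoint in SAP 2.2 is a subject-level outcome: "Development of specific anti-ALD403 antibodies". Immunogenicity of repeat doses is part of a secondary objective (SAP 1.1.2).

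SAP 3.6.5 summarises two groups in one table. The first is subjects with pre-existing antibodies. For the second, "the number and percent of subjects who develop anti-drug antibodies to ALD403 during the trial will be summarized at each scheduled visit". One denominator rule covers both: "Denominators for percentages will be the total number of samples taken for the specified visit". The only other antibody outputs are listings (SAP 3.6.3, 3.6.5 and 3.6.5.1).

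On sampling, SAP 2.2.4 says: "Serum blood samples will be taken pre-dose on Day 0, and Weeks 2, 4, 8, 12 (pre-dose), 24, and 32 or ET". That is one sample at each of Day 0 and six post-baseline time points. A further request goes only to those with a positive final result, who "will be asked to provide up to 2 additional blood samples for immunogenicity testing at 3 month intervals for up to 6 months". For the blinding and capture of those samples, the SAP points to a blinding plan.

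On windows, SAP 2.4 says: "Analysis Windows used to report non-diary endpoints are outlined in" Table 3. There the Week 24 window is Days 155 to 203. The Week 32 window is anything later than Day 204, with target Day 224 and no upper limit. Under the column headed "If more than one which one is used for analyses", post-treatment windows keep the value closest to the target day.

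**The concern.** The question a reader will ask is what proportion of treated subjects ever developed antibodies, by dose. The specified outputs do not answer it. A subject who is positive once and then reverts counts at one visit only, so responses at different visits never accumulate into a trial-level figure.

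Two features can also shift the visit percentages. Subjects already positive at baseline cannot newly develop antibodies, yet their samples count in the denominator for doing so. And the follow-up samples come only from subjects known to be positive, while nothing in the SAP keeps them out of the scheduled-visit windows that apply to antibody results.

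**Working it through.** The documents give no antibody rate, so there is no plan figure to reproduce. All positivity, withdrawal and baseline-prevalence values below are assumptions.

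**1. Any-time incidence from visit percentages.** Take 5% positive at each of the six post-baseline visits, with complete sampling.
- Same subjects positive each time: any-time = 5%.
- Different subjects each time: any-time = 6 × 5% = 30%.

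The visit table cannot distinguish these cases.

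**2. Baseline positives in the denominator.** If a fraction b is positive at baseline and 10% of the remainder develop antibodies, the reported value is 10% × (1 − b). For b = 2% it is 9.8%; for b = 10% it is 9.0%.

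**3. Completers at Week 32.** The visit falls on Days 217 to 231. With 90-day spacing (assumed), the follow-up samples fall on about Days 307–321 and 397–411. By date both lie in the open window, but the earliest is 307 − 224 = 83 days from target and the scheduled sample is at most 7 days away. Table 3 keeps the scheduled sample, so the rate is unchanged.

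**4. Early terminators.** If the ET visit is on Day E, follow-up samples fall on about E + 90 and E + 180.
- E = 100: Day 190 is in the Week 24 window and Day 280 is in Week 32. With no scheduled sample there, each becomes the visit value.
- E = 140: Day 230 becomes the Week 32 value.
- In general, the second sample falls after Day 204 when E is 25 or later (25 + 180 = 205).

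A subject negative at ET is not asked for these samples and contributes nothing to either window.

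**5. Size of the Week 32 bias.** Let w be the fraction leaving before the Week 32 window (with E at least 25), and p the positivity among both completers and early terminators. Assume every positive early terminator has a follow-up sample in the window that is still positive. Then

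reported = [(1 − w)p + wp] / [(1 − w) + wp] = p / (1 − w + wp).

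| p | w = 5% | w = 15% |
|---|---|---|
| 5% | 0.05/0.9525 = 5.25% | 0.05/0.8575 = 5.8% |
| 10% | 0.10/0.955 = 10.5% | 0.10/0.865 = 11.6% |
| 20% | 0.20/0.96 = 20.8% | 0.20/0.88 = 22.7% |

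The excess over p runs from about 0.25 to 2.7 percentage points. The Week 24 effect works in the same way but was not sized.

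**6. ET samples themselves.** An ET sample dated Day 99 to 154 falls in the Week 16 or Week 20 window, where the schedule has no antibody sampling. A response seen only there enters no percentage at a scheduled antibody visit.

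**The case against.** The best defence is that samples and subjects coincide: one antibody sample is scheduled per visit and one value is kept per window. SAP 3.6.4.3 uses a similar available-assessments denominator for ECGs. This stands for ordinary by-visit positivity.

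A reader might infer more: that dividing subjects by samples makes the rates wrong in general and dilutes Week 32. With about 700 ALD403 subjects (2 × 350) and two follow-up samples per positive, 10% would read 70/(700 + 140) = 8.3% and 20% would read 140/(700 + 280) = 14.3%. The documents do not support that reading. It needs every sample in the open window counted in the denominator while the numerator follows the closest-to-target rule. It also needs every positive to give both samples, which are only requested.

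The numerator might be read as cumulative, so that the Week 32 row already shows subjects who ever developed antibodies. The denominator would still be Week 32 samples. With 5–15% withdrawal, a true 10% would read 0.10/0.95 = 10.5% to 0.10/0.85 = 11.8%.

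The blinding plan, which was not available for this review, may deal with the follow-up samples. It is cited for blinding and capture, however, and the SAP's own tabulation rule is silent. Protocol 8.4.1 encourages subjects who stop treatment to continue assessments, which limits w. The listings allow an any-time count to be made by hand, and baseline positives appear in the same table, so a reader could adjust for them. Immunogenicity is descriptive and outside the testing hierarchy. These points lower the stakes but leave the endpoint without a specified subject-level summary.

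**Conclusion.** The concern holds in a limited form. The firmest part needs no assumption about windows: a listed endpoint under a secondary objective has no any-time incidence per subject, and the visit percentages cannot provide one. By contrast, SAP 3.6.6 does specify an ever-after-baseline summary for the C-SSRS.

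Keeping baseline positives in the denominator is a smaller matter, worth 0.2 to 1.0 percentage points on a 10% rate if 2–10% are positive at baseline.

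The window problem is real but confined to antibody-positive early terminators. Its 0.25 to 2.7 point size rests on 5–20% positivity, 5–15% early withdrawal, equal positivity in leavers and completers, and all follow-up samples given and still positive; incomplete or reverting follow-up would shrink it. It would be wrong to conclude that the immunogenicity rates as a whole are incorrect, or that completers' Week 32 rates are diluted. The change is worth making before unblinding, but efficacy conclusions do not depend on it.

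**What to change.** In SAP 3.6.5:
- **Per visit:** use as denominator the subjects with a reportable result from that visit's scheduled sample.
- **Development of antibodies:** use subjects negative at baseline with at least one reportable post-dose result, ET samples included. Add an any-time incidence row by dose group on that denominator.
- **Follow-up samples:** close the Week 32 window for immunogenicity. Tabulate the post-study samples separately as persistence among positives, outside all scheduled-visit percentages, including Week 24. Excluding them loses no new responder, since only subjects already positive are asked for them.

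When Table 3 is edited, assign Day 204 to a window; at present it falls between Week 24 and Week 32.

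The cost is SAP wording and one table row, with no new samples. The reported antibody rate may be slightly less favourable, because an any-time figure cannot be lower than a single visit's figure on the same denominator.

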3.6.5.1. Anti-ALD403 Antibody Analysis

Subjects with a positive anti-ALD403 antibody result will be listed.

3.6.6. Columbia-Suicide Severity Rating Scale (C-SSRS)

The C-SSRS assesses lifetime suicidality during an initial baseline evaluation, and then monitors suicidal ideation and suicidal behavior at subsequent follow-up assessments. Four constructs are measured. The first and second are the severity and intensity of ideation, rated on a 5-point ordinal scale. The third is the behavior subscale, which is rated on a nominal scale and the fourth is the lethality subscale, which assesses actual attempts. These results will be reported at baseline and post baseline. Results for individual time points will be provided in a listing.

The denominator for percentages will be the number of subjects with a C-SSRS assessment at baseline or at any time post baseline. The post baseline summary will list a subject as yes if they ever selected yes after baseline.

3.6.7. Pregnancies

Positive pregnancy test results will be listed.

